1.2 OBJECTIVES

1.2.1 Primary objectives

The primary objective of this study is to show the contribution of OZ439 to the clinical and parasiticidal effect of OZ439/FQ combination by analyzing exposure-response of OZ439 measured by Day 28 PCR-corrected ACPR for the effect and the AUC of OZ439 as PK predictor

1.2.2 Secondary objectives

The secondary objectives of this study are:

- To evaluate the dose response of OZ439 combined with FQ on PCR-corrected and crude Day 28 ACPR
- To evaluate the dose-response of OZ439 combined with FQ on selected secondary endpoints
- To evaluate the safety and tolerability of different dosages of OZ439 in combination with FQ and FQ alone
- To characterize the PK of OZ439 in plasma, and of FQ and its active metabolite SSR97213 in blood

1.2.3 Tertiary/exploratory objectives

The exploratory objectives of this study are:

- To explore the impact of study treatment on functional gametocytemia
- To evaluate the relationship between parasitemia and concentration of OZ439/FQ
- To evaluate the relationship between QTc and concentration of OZ439/FQ

1.3 DETERMINATION OF SAMPLE SIZE

The strategy for selecting fixed FQ dose, baseline parasitemia, and sample size was composed of two parts:

1. Estimated efficacy (Day 28 PCR-corrected ACPR) of FQ 200, 400, 600 and 900 mg administrated in presence of OZ439 TPGS for different levels of baseline parasitemia
2. Estimated power for various sample size of an OZ439 exposure-effect analysis, considering the fixed FQ dose, the 4 selected OZ439 dose levels (0, 300, 600, 1000 mg) and the selected baseline parasitemia

Part 1: Estimated efficacy (Day 28 PCR-corrected ACPR) of FQ 200, 400, 600 and 900 mg administrated in presence of OZ439 TPGS for different levels of baseline parasitemia

Clinical trial simulations were used, consisting of simulating FQ concentrations at Day 7, baseline parasitemia, and then PCR-corrected ACPR at Day 28 using a model linking ACPR at Day 28 probability to FQ concentration at Day 7 and baseline parasitemia.

The model (eq 1) was a logistic regression modeling PCR-corrected ACPR at Day 28 probability (p) as a function of FQ concentration at Day 7 ($\text{Conc}_{D7,FQ}$), Artesunate (AR) indicator (no/yes) and baseline \log_{10} -parasitemia. It was developed from DRI10382 data: African patients, Per Protocol population, excluding patients with reinfections, using the 4 arms of the DRI10382 (FQ 4 mg/kg or AR + FQ 2, 4 or 6 mg/kg, repeated doses). Two types of analyses were done, classifying as failure or excluding patients with rescue therapy before/without failure, and finally the results of the analysis excluding patients were favored, to compensate for the possible underestimation of FQ single dose effect (model built on repeated doses). In this analysis based on 223 patients, the FQ efficacy was estimated to be $\text{ACPR28corr}=80.9\%$ (95% Confidence Interval [CI]: 66.7% to 90.9%) in arm FQ 600 mg.

$$(eq\ 1)\ \log(p/(1-p)) = \alpha + \beta_{FQ} \cdot \text{Conc}_{D7,FQ} + \beta_{AR} \cdot (\text{AR}=\text{yes}) + \beta_{BasePar} \cdot \log_{10}(\text{BasePar})$$

FQ concentrations at Day 7 (168 h post dose) were simulated from the FQ PopPK model updated from DRI12805 (POH0456) for TPGS formulation and single dose administration, in an African adult population (weights resampled from 194 profiles of African adults of DRI10382 and DRI12805 cohort 1A and 1B, of median weight 55 kg and median age 21 years). Log-normal distributions were fitted to these simulated concentrations and then used for simulation.

Baseline parasitemia was simulated for different scenarii, using truncated log-normal distributions. The base assumption was a baseline parasitemia greater than 1000 parasites/ μ L and of median about 10,000 parasites/ μ L. Some other scenarii were considered: baseline parasitemia greater than 3000, 5000, or 10,000 parasites/ μ L, with a maximum fixed at 5.5 log₁₀ parasites/ μ L. In the following, the baseline parasitemia greater than 3000 parasites/ μ L scenario was selected to ensure a better enrollment of patients during the study.

Based on N=10,000 simulations/arm and S=1000 simulations for the model parameters uncertainty, the results showed a PCR-corrected ACPR at Day 28 estimated at 72% (90%CI: [57% to 84%]) for FQ 400mg alone and 79% (90%CI: 67% to 87%) for FQ 600 mg alone for a baseline parasitemia greater than 3000 parasites/ μ L. Finally the FQ fixed dose of 400 mg was selected.

Results estimated that 30 evaluable participants per treatment arm will yield a power around 90% to detect an OZ439 concentration effect relation (in a population of patient with a baseline parasitemia greater than 3000 parasites/ μ L, for 4 arms FQ 400 mg + OZ439 at 0, 300, 600, and 1000 mg).

Part 2: Estimated power for various sample size of an OZ439 exposure-effect analysis, considering the fixed FQ dose, the 4 selected OZ439 dose levels (0, 300, 600, 1000 mg) and the selected baseline parasitemia

Simulation of clinical trials

Clinical trial simulations were used to simulate trials of 4 arms with a fixed dose of 400 mg FQ and 4 dose levels of OZ439 (0, 300, 600, and 1000 mg) for a baseline parasitemia greater than 3000 parasites/ μ L. FQ and OZ439 concentrations at Day 7 (168 h post dose) were simulated using log-normal distributions that were corrected to concentrations obtained from the FQ PopPK model and from the OZ439 PopPK model in an African adult population (as in part 1), and were assumed to be slightly correlated. Truncated log-normal distributions were used to simulate baseline parasitemia greater than 3000 parasites/ μ L in log₁₀Par/ μ L by a normal distribution:

mean=4, SD=0.55, minimum=3.48; maximum=5.5 (minimum and maximum for the truncation). Day 28 PCR-corrected ACPR was simulated using a “hypothetical” model linking ACPR at Day 28 probability to FQ and OZ439 concentration at Day 7 and baseline parasitemia.

The “hypothetical” logistic regression model (eq 2, see below) used for simulations was a composite of the “PQP/OZ-ACPR28 model” built by MMV, modeling PCR-corrected ACPR at Day 28 probability (p) as a function of OZ439 and PQP concentrations at Day 7 and baseline log₁₀-parasitemia, and of assumptions made on FQ efficacy, which were based on the results of part 1. Precisely, β_{FQ} was fixed at 0.12 by calibration to get ~ 72% success ACPR at Day 28 for FQ 400 mg alone for a baseline parasitemia greater than 3000 parasites/ μ L, and the following parameters were extracted from the MMV model: $\alpha=3.23$, $\beta_{OZ439}=0.73$, and $\beta_{BasePar}=-1.27$.

$$(eq\ 2)\ log(p/(1-p)) = \alpha + \beta_{FQ} \cdot \text{Conc}_{D7,FQ} + \beta_{OZ439} \cdot \text{Conc}_{D7,OZ} + \beta_{BasePar} \cdot \log_{10}(\text{BasePar})$$

Using all these assumptions, the PCR-corrected ACPR at Day 28 rates simulated in the 4 arms FQ 400 mg + OZ439 at 0, 300, 600 and 1000 mg were of 72%, 81%, 91%, and 97% for a baseline parasitemia greater than 3000 parasites/ μ L.

Clinical trials analyses

Exposure-effect analyses of the simulated clinical trials were performed, consisting of a logistic regression model of exposure at Day 7 for both drugs, with baseline parasitemia as covariate, and the Day 28 PCR-corrected ACPR as response variable (as in eq 2 above). Significance of OZ439 concentration effect (β OZ439) was analyzed using a 2-sided alpha Wald test at 5%.

Overall, five thousand trial simulations were performed, and the power was deduced as the percentage of significant simulated trials. Results estimated that 30 evaluable participants per treatment arm will yield a power around 90% to detect an OZ439 concentration effect relation (in a population of patients with a baseline parasitemia greater than 3000 parasites/ μ L, for 4 arms FQ 400 mg + OZ439 at 0, 300, 600, and 1000 mg).

1.4 STUDY PLAN

A brief description of the study design is provided in [Section 1.1](#). The planned study schedule can be found in [Appendix A Schedule of Activities](#) of the protocol.

1.5 MODIFICATIONS TO THE STATISTICAL SECTION OF THE PROTOCOL

The statistical section of the protocol was never changed in an amendment.
There are no planned interim analyses.

1.6 STATISTICAL MODIFICATIONS MADE IN THE STATISTICAL ANALYSIS PLAN

The primary efficacy population will be the PK/PD population instead of the mITT population stated in the protocol.

A per-protocol [PP] population was added in order to align the analysis population with the primary endpoint of the study. All populations have been further clarified from the protocol definitions

The derivation of the secondary endpoint, Fever clearance time (FCT), has been added. FCT will be assessed by measuring the time from the first dose until the first time that the body temperature dropped and remained <37.5 °C.

Time to 50% parasite reduction (T_{PC50}) will also be calculated in addition to the time to 99% PR.

The evaluation of the relationship between parasitemia (as measured on thick blood film and/or by qPCR) and concentration of OZ439/FQ may be performed in a separate analysis pooling data from different studies and be reported in a separate report.

The terminal half-life ($t_{1/2}$) for OZ439 and ferroquine will not be estimated as this endpoint does not contribute to the objectives of the study.

The definition of baseline to be used for efficacy analyses has been clarified.

2 STATISTICAL AND ANALYTICAL PROCEDURES

2.1 ANALYSIS ENDPOINTS

2.1.1 Baseline

Baseline for all efficacy analyses will be defined as the last measurement prior to the study drug administration, i.e., in general the Day 0, pre-dose assessment. Only if the Day 0, pre-dose assessment is missing the screening assessment will be used instead.

For safety analyses baseline is defined as the last available value before first IMP at Visit 1 (screening) for laboratory and vital signs and at Visit 2 (Day 0 before IMP administration) for ECG parameters

2.1.2 Demographic and baseline characteristics

All baseline safety and efficacy parameters (apart from those listed below) are presented along with the on-treatment summary statistics in the efficacy and safety sections (Section 2.4.4 and Section 2.4.5).

The below variables will be summarized by treatment group and, overall.

Demographic characteristics

Demographic variables at baseline:

- Age (years)
- Gender (Male, Female)
- Race (American Indian or Alaska Native, Asian, Black or African American, Native Hawaiian or Other Pacific Islander, White, Not Reported and Unknown)
- Ethnicity (Hispanic, Not Hispanic)
- Body weight (kg)
- Body weight category : [35-40 kg], [40-50 kg] and > 50 kg
- Body mass index (BMI) (kg/m²)
- Fever (yes/no) defined with axillary temperature \geq 37.5 degree Celsius (°C) or oral/ rectal/ tympanic temperature \geq 38°C
- Baseline parasitemia (parasites/ μ L)
- Baseline parasitemia defined in 4 classes : (< 3000 parasites/ μ L, [3000-10000] parasites/ μ L, [10000-50000] parasites/ μ L and > 50000 parasites/ μ L)

Medical or surgical history

Medical and surgical history, other than malaria, within the life-time of the patient, will be coded to a preferred term (PT) and associated primary System Organ Class (SOC) using the version of the Medical Dictionary for Regulatory Activities (MedDRA) in use at Sanofi at the time of database lock (DBL).

Disease characteristics at baseline

Clinical signs/symptoms related to uncomplicated malaria and other relevant signs of malaria will be coded to PT using the version of MedDRA in use at Sanofi at the time of DBL.

Any technical details related to computation, dates, and imputations for missing dates are described in Section [2.5](#).

2.1.3 Prior or concomitant medications

All medications taken within 2 months prior to the screening visit, and during the study until the end of the study (Day 28) are to be reported in the electronic case report form (e-CRF) pages.

All medications will be coded using the World Health Organization-Drug Dictionary (WHO-DD) version in effect at Sanofi at the time of database lock.

- Prior medications are those the patient used prior to screening up until the first investigational medicinal product (IMP). Prior medications can be discontinued before first administration or can be ongoing during treatment phase.
- Concomitant medications are any treatments received by the patient concomitantly to the IMP, from randomization (Day 0) to Day 28. A given medication can be classified both as a prior medication and as a concomitant medication. Concomitant medications do not include medications started during the post-treatment period (as defined in the observation period in Section [2.1.5](#)).
- Post-treatment medications are those the patient took in the post-treatment period (as defined in the observation period in [Section 2.1.5](#)).

Any technical details related to computation, dates, imputation for missing dates are described in Section [2.5](#).

2.1.4 Efficacy endpoints

All efficacy measurements, scheduled or unscheduled, or done out of the time window (see details in the last paragraph of this section), will be assigned to analysis windows defined in [Section 2.5.4.1](#). For all post baseline measurements, the value used for the analyses at a given time point is the value obtained within the corresponding analysis windows.

At screening/pre-dose blood films, three slides (two thick films and one thin film) should be collected using the same blood sample at the site, before Informed Consent signature, according to local standard procedures and within 4 hours prior to dosing, can be used for screening/pre-dose parasitemia assessment.

- The parasite count from the first thick film will be used to calculate the screening parasitemia value.
- The second thick film slide will be used to calculate a more accurate pre-dose parasitemia count (asexual).
- The thin film slide is used for parasite speciation. Only patients with *P. falciparum* monoinfection should be recruited in the study.

The baseline value for efficacy variables is defined as the last available value on or before randomization. By default, the baseline parasitemia is the parasite count based on the second thick film slide, even if missing value at screening.

Time points and imputation rules

Parasite count (i.e. asexual forms *P. falciparum* parasite count determined from blood thick films at each planned time point, a second thick film slide is kept as contingency) and concomitant body temperature are the key components of efficacy evaluations. They have to be assessed at predefined time points specified in the study protocol. However, shifts from scheduled timing are expected (especially after discharge from hospital), and this will be managed in analyses by allocating protocol planned time points based on the actual timing of assessments - rather than based on the theoretical timing of the visit they come from, using allowed windows of time around these protocol planned time points. Allowed time windows are defined in [Section 2.5.4.1](#). In this section and other sections related to efficacy, time points will always refer to these allowed time windows, except otherwise specified.

In addition, except where otherwise specified, the following imputation rules will apply in case of missing or out of time window parasite count at a protocol scheduled time point, where the missing count occurs before rescue treatment start, before or on Day 28, or in absence of concomitant fever. In such cases, the missing parasitemia will be considered as:

- positive, if followed or preceded by positive parasitemia,
- negative, if preceded and followed by negative parasitemia,
- missing, if no parasite count available thereafter.

In above bullets:

- positive parasitemia means *P. falciparum* parasite count from thick film ≥ 1 parasite/ μ L, otherwise the parasitemia is negative.
- parasite count from thick film performed after rescue treatment start cannot be used for imputation of missing or out of time window parasite count.

- parasite count from thick film performed the day of rescue treatment start can be used for imputation because this is regarded as before rescue treatment.

In case of concomitant fever related to malaria event (fever is defined in [Section 2.1.4.2.8](#)), a missing parasitemia will be always considered as positive.

In case of missing (or out of time window) parasite count at successive protocol scheduled time points, the above imputations rules could be extended after endorsement of the imputations by the clinical team, otherwise the case will be classified as a deviation preventing evaluation of ACPR as listed in [Section 2.3.2.2](#). Cases of missing body temperature concomitantly with positive parasitemia (observed, or put in place of a missing parasite count as explained above) will be imputed, according to the same principle as for parasitemia imputations, after endorsement of the imputations by the clinical team, or will be classified as deviation.

Efficacy evaluation

Efficacy evaluation will use Early Treatment Failure (ETF), Late Clinical Failure (LCF), Late Parasitological Failure (LPF), and Adequate Clinical and Parasitological Response (ACPR) definitions given below.

Table 1 - Revised WHO classification of treatment failures in areas of intense malaria transmission

Criterion
ETF is defined as one of the following :

- Development of danger signs or symptoms of complicated/severe malaria on Day 1, Day 2 or Day 3, in the presence of parasitemia (reported as Term='Complicated Malaria' by the investigator in the 'Adverse Event' form and reported in the e-CRF dedicated form "Malaria Signs and Symptoms") concomitant to at least one positive parasitemia. Considering that the drug cannot be active before 24h, a severe malaria presenting between 0h and 24h is highly suspect of wrong inclusion of the patient.- Parasitemia on Day 2 higher than baseline parasitemia count (irrespective of body temperature)- Parasitemia on Day 3 with axillary temperature of $\geq 37.5^{\circ}\text{C}$- Parasitemia on Day 3 $\geq 25\%$ of baseline parasitemia count
LCF is defined as one of the following, without previously meeting any of the ETF criteria :

- Development of danger signs or severe malaria after Day 3 in the presence of parasitemia (reported as Term='Complicated Malaria' by the investigator in the 'Adverse Event' form and reported in the e-CRF dedicated form "Malaria Signs and Symptoms") concomitant to at least one positive parasitemia.- Presence of parasitemia and axillary temperature $> 37.5^{\circ}\text{C}$ on any day from Day 4 to Day 28, without previously meeting any of the criteria of early treatment failure
LPF

- Presence of parasitemia on any day from Day 7 to Day 28, and axillary temperature $< 37.5^{\circ}\text{C}$, without previously meeting any of the criteria of ETF or LCF

Criterion

ACPR

- Absence of parasitemia on Day 28 irrespective of axillary temperature without previously meeting any of the criteria of ETF or LCF or LPF, and without previous rescue therapy start. Rescue therapy start without previous WHO criteria can be due to: investigator decision (classified as failure or deviation based on case by case clinical review, see [Section 2.3.2.2](#)), major vomiting or severe malaria at Day 0 (both classified as deviation, see [Section 2.3.2.2](#)), other species infection.

The following definitions will also be considered regarding efficacy evaluation:

Re-emergence / Recurrence (recrudescence and re-infection): The appearance of asexual parasites after clearance of initial infection irrespective of genotype.

Recrudescence: The appearance of asexual parasites after clearance of initial infection with a genotype identical to that of parasites present at baseline. Recrudescence is confirmed by microscopy (positive blood smear) and by genotyping PCR analysis.

Re-infection: The appearance of asexual parasites after clearance of initial infection with a genotype that differs from that of parasites present at baseline. Re-infection is confirmed by microscopy (positive blood smear) and by genotyping PCR analysis.

Treatment failure: Any patients who met any of the criteria for ETF, LCF or LPF.

Crude ACPR does not distinguish between re-infection (by a new clone of parasite) and recrudescence (re-emergence of the original clone of parasite that was present at baseline); i.e. presence of either a new clone or genotypically identical parasite will be considered a treatment failure.

PCR-corrected ACPR applies only to recrudescence; (i.e. patients with re-infection are considered non-evaluable for the analysis of PCR-adjusted ACPR). Presence of a genotypically identical parasite will be considered a treatment failure.

Genotyping adjustment

LCF occurring from Day 7 or LPF will be sub-classified as follows using parasite genotyping results:

- *P. falciparum* recrudescence, if no other species reported in eCRF and genotyping result is “recrudescence”
- *P. falciparum* reinfection, if no other species reported in eCRF and genotyping result is “reinfection”

- Other species with *P. falciparum* recrudescence, if other species reported in eCRF and genotyping result is “recrudescence”
- Other species with *P. falciparum* reinfection, if other species reported in eCRF and genotyping result is “reinfection”
- Undetermined, negative or missing PCR, if genotyping result is “Undetermined”, “negative”, “undetermined” or “missing”, with or without other species infection.

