2.1.4.2.4 Re-emergence time

Timing to consider

In this section, except otherwise specified, the post-dose timing associated to parasitemia will refer to:

- its assigned time point as defined in [Section 2.5.4.1](#), if it exists,
- its actual post-dose timing as defined in [Section 2.5.4.1](#) and expressed in days, if outside defined time windows.

Establishing re-emergence

The re-emergence is defined as the re-appearance of asexual forms of *P. falciparum* irrespective of genotype after clearance of initial infection. Blood thick films performed before Hour 24 (Day 1) time point will not be considered for re-emergence screened.

Time to re-emergence

The time to re-emergence will be the post-dose timing associated to the first positive - observed or imputed - parasitemia after clearance. For patient not reaching parasite clearance of initial infection, the time to re-emergence will be equal to zero.

In patients having reach parasite clearance of initial infection, in case a rescue therapy would be started without previous re-emergence or other species infection, then the time to re-emergence will be the time point of the rescue therapy start. If the case has been classified as a protocol violation, then the time to re-emergence will be censored at the time of the rescue start.

Otherwise, the time to re-emergence will be censored at the post-dose timing associated to the last available patient's thick film before withdrawn (for any reason), or, on/before start of a rescue therapy for other species infection, whichever comes first.

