From Day 4, time points assigned to scheduled or unscheduled parasitemia, body temperature will be based on the actual day of assessment and allowed time windows, as specified in Table 4.

Table 4 – Time windows definition from Day 4

Protocol planned time point	Allowed deviation from targeted time	Corresponding window of time for actual blood film timing
Hour 96 (Day 4)	0	Day 4
Hour 120 (Day 5)	0	Day 5
Hour 144 (Day 6)	0	Day 6
Hour 168 (Day 7)	0	Day 7

Day 10	±1 days (included)	9 days to less than 11 days
Day 14	±1 days (included)	12 days to less than 15 days
Day 21	±2 days (included)	19 days to less than 23 days
Day 28	±2 days (included)	26 days to 30 days

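### For ACPR, a film read outside its time window is imputed as if missing, and three Table 4 windows contradict their own tolerance, so a read negative can become an imputed positive

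*SAP*

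**What the plan says.** SAP 2.1.4 first says that all efficacy measurements, including those done out of window, will be assigned to the windows of 2.5.4.1. It then says: "For all post baseline measurements, the value used for the analyses at a given time point is the value obtained within the corresponding analysis windows". Under the time-point and imputation heading, "the following imputation rules will apply in case of missing or out of time window parasite count at a protocol scheduled time point". The value becomes "positive, if followed or preceded by positive parasitemia"; "negative, if preceded and followed by negative parasitemia"; and "missing, if no parasite count available thereafter". The only films barred from use in imputing are those after rescue: "parasite count from thick film performed after rescue treatment start cannot be used for imputation". Nothing says whether the out-of-window film may serve as a neighbour for its own time point.

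SAP 2.5.4.1 sets the windows. Table 3 covers Hours 6 to 72. For Table 4, "From Day 4, time points assigned to scheduled or unscheduled parasitemia, body temperature will be based on the actual day of assessment".

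Two secondary endpoints are handled differently. Time to parasite clearance (2.1.4.2.3) uses no imputation, except for a missing film with fever, and keeps the actual time of an out-of-window film. Time to re-emergence (2.1.4.2.4) also uses actual timing, "expressed in days, if outside defined time windows", but accepts an imputed positive as the event.

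**The concern.** A film taken an hour or a day off schedule still shows whether parasites were present. Treating it as if it had never been taken discards information, and the rule is asymmetric: one positive neighbour gives a positive, whereas a negative needs two negative neighbours. The error therefore tends to produce parasitemia that the microscopist did not see. SAP 2.4.4.1.1 sends missing Day 28 parasitemia in the primary analysis to these same rules, so the effect reaches PCR-corrected ACPR.

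The SAP itself expects shifts in timing, especially after discharge. Where successive films are missing or out of window, it relies on endorsement by the clinical team. The trial is open label (Protocol 7.4), so a complete prespecified rule is worth more than case-by-case judgement.

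**Working it through.** **Inputs.** Windows and allowed deviations: SAP 2.5.4.1, Tables 3 and 4. Visit tolerances: the protocol's Schedule of Activities (Day 14 ±1, Day 21 ±2, Day 28 ±2). Imputation rules: SAP 2.1.4. Outcome classes: table in SAP 2.1.4.1. Planned response rates: Protocol Appendix 8 (72%, 81%, 91% and 97%, with 30 evaluable per arm). From Day 4 the actual day is taken as a whole number (assessment date minus dosing date).

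**Step 1. Rebuild each window as target minus/plus the allowed deviation.** All 8 rows of Table 3 reproduce. In Table 4, 5 of 8 rows reproduce and these three do not:

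| Row | Allowed deviation | Implied days | Stated window | Days in stated window |
|---|---|---|---|---|
| Day 10 | ±1, included | 9–11 | 9 to <11 | 9–10 |
| Day 14 | ±1, included | 13–15 | 12 to <15 | 12–14 |
| Day 21 | ±2, included | 19–23 | 19 to <23 | 19–22 |

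A Day 14 visit made on Day 15, or a Day 21 visit made on Day 23, complies with the protocol but is out of window in the SAP.

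**Step 2. Coverage.** The gaps in Table 3 are 8–11, 14–17, 20–23, 26–29, 32–34, 39–45 and 51–68 h: 3+3+3+3+2+6+17 = 37 of the 71 h from Hour 5 to Hour 76. Over Days 4–30, the stated windows leave out Days 8, 11, 15–18 and 23–25 (9 of 27). With the three rows corrected, Days 8, 12, 16–18, 24 and 25 (7 of 27) are still uncovered.

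**Step 3. Apply the rule.**

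*Day 23 film.* Day 14 is negative. The Day 21 visit is made on Day 23, with no fever and a negative film. Day 28 is positive and genotyped as reinfection.
- As observed: reinfection on Day 28, a success in both columns of 2.1.4.1.
- By the rule, if the Day 23 film may not be a neighbour: the film before is negative and the next is the positive Day 28 film, so Day 21 is imputed positive. That is reinfection before Day 28: excluded in the per-protocol column, failure in the mITT column. If the imputed positive is instead classed as having no PCR result, the entries are the same.
- By the rule, if it may be a neighbour: negative before and negative after, so Day 21 is negative and the success stands.

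*72 h film.* Hour 48 is positive. The Hour 72 film is taken at 77 h, outside 68–76 h, and is read negative. The positive predecessor is sufficient, so Day 3 is imputed positive whichever way the neighbour question is settled. With an axillary temperature of at least 37.5 °C assigned to Day 3, this is early treatment failure, a failure in both columns. Without fever, the imputed value carries no count, cannot meet the 25%-of-baseline criterion, and does not by itself make a failure.

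**Step 4. Size.** Planned failures: 30 × (0.28 + 0.19 + 0.09 + 0.03) = 30 × 0.59 = 17.7. One added failure is 1/17.7 = 5.6% of the events.

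For illustration only, a logistic model on dose with the planned rates and a two-sided 5% Wald test gives about 87% power, against the plan's figure of around 90%. The plan's simulated concentrations are not given, so that figure cannot be reproduced exactly. If 2%, 5% or 10% of true successes were turned into failures (assumed rates; about 2, 5 or 10 of 120 − 17.7 = 102.3), power would be about 81%, 71% or 61%. The documents give no such rate.

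**The case against.** - *The SAP does not clearly tell the analyst to discard results.* Its opening sentence assigns out-of-window measurements to windows. This stands in part: the two statements conflict. But 2.5.4.1 offers no window for a film in a gap, and 2.5.4 leaves out-of-window handling to the dedicated sections. For ACPR that is the imputation text in 2.1.4.
- *The 72 h example is unusual.* A patient still positive at 48 h may stay in hospital for up to 4 days, and a first negative film must be confirmed 6 to 12 hours later. The wording on fever is also unclear. The three rules may be meant only for patients without fever, and the separate fever sentence names only missing parasitemia. Temperature takes its time point from the film, so it may lose its Day 3 label too. All of this is fair, and it limits how often the example leads to early treatment failure. It does not protect the read negative.
- *Late, uncleared infection is well sampled.* Protocol 9.1.1.3 asks for films at least every 8 hours if parasites have not cleared by 72 h, so an unscheduled film may fill a Day 4 to Day 7 window. This stands.
- *Gap days are not patients.* Most gap days have no scheduled visit. This stands; the coverage figures show opportunity, not frequency.

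A reader might go further and infer that a true recurrence in a gap, say an unscheduled positive film on Day 17, drops out of ACPR. The documents do not support that. Late clinical and late parasitological failure are defined on any day (SAP 2.1.4, Table 1), imputation applies only at scheduled time points, and the sentence tying efficacy time points to the windows allows exceptions. What remains is that this sentence and the any-day definitions need reconciling. Nor is it right that only 68–76 h is covered between 51 and 96 h: from Day 4 the calendar day applies, which for most dosing times begins before 96 h.

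**Conclusion.** The point holds for ACPR. As written, the rule can replace a known negative with an imputed positive and change a patient's class on the primary endpoint. Three Table 4 rows are inconsistent within themselves, and two of them put protocol-compliant films out of window. The Day 23 example needs no protocol departure, but it does depend on the unstated neighbour rule. The 72 h example does not depend on the neighbour rule, but it needs a late film, and fever if it is to count as a failure.

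The number of patients affected is unknown. Each added failure would be between 5% and 6% of about 18 planned events; a per-protocol exclusion instead removes a success. A reader might infer that the misclassification falls mainly on the low-OZ439 arms; this is plausible if clearance is slower there, but the documents do not show it. The conclusion rests on reading Table 4 by whole days and taking neighbours as the nearest usable films.

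**What to change.** In SAP 2.1.4, state that a film read before rescue is never replaced by imputation. It keeps its result and its actual day for early failure, late failure and ACPR, as out-of-window films already do for clearance and re-emergence times, and it may serve as a neighbour. Impute only where no film was read.

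Correct the Day 10, Day 14 and Day 21 rows of Table 4 to match their stated deviations. Correcting the table alone is not enough, since 7 of 27 days stay uncovered.

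Reconcile four statements: the opening of 2.1.4, its imputation rules, the any-day failure definitions in Table 1, and the re-emergence rule in 2.1.4.2.4, which lets an imputed positive be the event.

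The cost is SAP wording and programming, with no new data. The downside is small: a few values will come from slightly off-target times.
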